#### 2. Design

2.1. What research methods will be used in the project? Check all that apply.

| Surveys/Questionnaires  | Interviews    | Audio Taping                          |
|-------------------------|---------------|---------------------------------------|
| Behavioral Observations | Chart Reviews | Video Taping                          |
| Focus Groups            | Randomization | Double-Blind                          |
| Control Group           | Placebo       | Withhold/Delay Treatment              |
| Specimen Collection     | Deception     | Telephone Survey                      |
| Other (Describe)        |               | · · · · · · · · · · · · · · · · · · · |

2.2. Describe how randomization or other treatment assignment will be made. The RCT will involve random assignment of 250 consenting subjects at the Cpl.

Michael J. Crescenz VAMC, and 100 at the VA TVHS . For practical reasons,

neither subjects nor the intervention providers will be blinded to subject assignment. Subject assignment will be a 50/50 ratio to V-WHI care or BHL usual care (no V-WHI care). Participants are not required to engage in BHL clinical care. Both groups are permitted to use other services through their own VA or other insurance coverage or out-of-pocket expenditures. With attrition at our site, we expect 225 at initial follow-up (month 4 to 5) and 200 at final follow-up (month 9); attrition rates of 10% and, in total, 20%.

The randomization procedure will be automated within full/part-time group using a block randomization technique within group, where part-time is defined as less than 30 hours per week. Each block of 4 will contain 2 V-WHI and 2 BHL, randomly ordered. The small block sizes assure an even flow of new cases to the counselors.

- 2.3. For retrospective research studies, provide the "look-back" period. (e.g., December 1, 1999 through December 31, 2008.) N/A
- 3. **Study Duration** 
  - Provide the estimated length of time to enroll all subjects and complete the study. 44 3.1. months will complete subject data collection; 48 months will complete analysis, reporting, and dissemination.

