The V-WHI may also involve referring clients to appropriate sources of care and resources within the VA. For example, in the course of providing the V-WHI interventions, the counselor may become aware of concurrent health, mental health (e.g., PTSD) and/or treatment issues (e.g., an evolving substance abuse disorder) that require separate attention. Should any indication of suicide risk arise it is addressed with appropriate clinical interventions. In such cases, the counselor may elect to notify the BHL or MH provider who can coordinate the necessary care. Finally, subjects in the V-WHI do not have to be taking an antidepressant and/or participating in psychotherapy. All subjects, regardless of group, are free to participate in any care they wish to use.

1.2. Explain if and how the follow-up of subjects will occur. Research follow-up visits can be completed over the telephone or in person. At the end of the first intervention period, which is month 4 to 5, all subjects will be invited to complete the first follow-up survey (T1). At month 9 (T2), all subjects will be invited to complete a final follow-up survey. To encourage subjects to complete each questionnaire on time, we will offer a \$25 incentive for baseline and T1 assessment points, and a \$45 incentive for completing the T2 assessment point. Additionally, reminder letters are mailed out shortly before each questionnaire is due and, if the person is late in responding, reminder calls will be made by the study research assistant.

1.3. Describe where, how and who will be conducting study procedures.

The V-WHI will be provided by counselors at the CMCVAMC who have successfully completed the training provided by the Tufts team. The baseline and

follow-up surveys will be completed by a research assistant at the CMCVAMC. V-WHI care is entirely telephonic. The research baseline and follow-ups can be telephonic and/or in-person. Cpl. Michael J. Crescenz based V-WHI Counselors and research staff completing study visits are approved on both the CMCVAMC and VA TVHS research staff forms.

- 1.4. If a survey study, specify the estimated amount of time that subjects will need to complete the questionnaires/tools. The baseline and follow-up research questionnaires will take approximately 45 minutes to complete.
- 1.5. If a blood draw, specify the amount of blood to be drawn in milliliters and in teaspoonfuls or tablespoonfuls and specify how often and where the blood will be drawn. N/A

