# (presenteeism) will be measured using the WLQ 8-item short form, which is already part of the BHL clinical assessment.

- 2.4. Not Applicable; subjects not recruited; chart review.
- 3. If applicable, indicate what populations will be targeted for recruitment as participants. Check all that apply.

| Males                        |           |
|------------------------------|-----------|
| Females                      |           |
| Inpatients                   |           |
| Outpatients                  | $\square$ |
| VA Employees                 |           |
| Non-English Speaking**       |           |
| Veteran Family members***    |           |
| Non-Veterans***              |           |
| Other (Specify)              |           |
| Not Applicable, chart review |           |

- 3.1. \*\*For non-English speaking subjects If an investigator proposes to use a participant population that does not speak or read English, a copy of the translated document, as well as the English version, needs to be forwarded to the IRB for approval. Translator certification is also required.
- 3.2. \*\*\*If non-veterans will be recruited for this study, explain why sufficient veterans are not available to participate in the project [VHA Handbook 1200.5, paragraph 16a]. Veteran's spouses/partners, caregivers, etc. are considered non-veterans for the purposes of this study.
- 3.3. \*\*\*Has approval to recruit non-veterans been received from the ACOS/R&D and Medical Center Director?
  - 3.3.1. Xot Applicable
  - 3.3.2. Pending (Non-veteran forms should be used. IRB office will obtain approval from ACOS/R&D and Medical Center Director.)
- 4. **Does this project target a specific race or ethnic group as participants?** [YES ] NO lf yes, check all that apply.

| Race                                      | Ethn  |
|---|-------|
| American Indian or Alaskan Native         | Hispa |
| Asian                                     | Not I |
| Black or African American                 | Othe  |
| Native Hawaiian or other Pacific Islander |       |
| Black, not of Hispanic origin             |       |
| White, not of Hispanic origin             |       |
| Other                                     |       |
|   |       |

| Ethnicity              |  |
|------------------------|--|
| Hispanic or Latino     |  |
| Not Hispanic or Latino |  |
| Other                  |  |
|                        |  |
|                        |  |
|                        |  |

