**Power Analysis and Sample Size** 

In this study, we wish to power the study to obtain an effect size that represents a minimally clinically important difference on the health outcomes and an economically important difference related to work productivity impact (the primary endpoint). Currently, MCID is established for the PHQ-9(2) and the PCS and MCS for the VR-12.

For the PHQ-9, we anticipate that the average subject will have an average baseline score of 15 on a 0-27 scale. A clinically-meaningful reduction of 5 points, which is stated in the literature, would have 100% power to be detected. For PCS and MCS, a clinically-meaningful 5-point improvement would afford 99% power.

With regard to Hypothesis 2, corresponding to the study's power to detect an economically important difference, the primary criterion is whether an ROI greater than 1 can be obtained. This analysis is described in the following section.

For presenteeism, a reduction of 1.2% in productivity loss (or a relative improvement of 1.2%) would have comparable value to the maximum expected cost of treatment, meaning that the economic value of treatment would exceed the cost. A sample size of 100 treatment and 100 controls after subject dropout would achieve an 83% power for this outcome. To be sure of getting these numbers based on previous success rates, we will recruit 250 subjects prior to 50-50 randomization within full time and part time strata.

4.2. Define plans for data and statistical analysis, including key elements of the statistical plan, stopping rules and endpoints.

In this section, we describe the methods for testing hypothesis 1, several additional analyses including testing related to the secondary study outcomes and sensitivity testing related to both the primary and secondary study endpoints and statistical power calculations. Following this section, there is a description of the methods for testing hypothesis 2, which consists of the ROI analysis.

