## PL1 = b\*PL0 + g\*X + c\*I(V-WHI) + error

where PL0 refers to the baseline WLQ productivity loss and PL1 refers to the post-treatment WLQ productivity loss, X represents a set of covariates such as full-time or part-time stratum assignment, age, gender, baseline depressive symptom severity and, prior depression, and, g represents their regression coefficients, and I(V-WHI) indicates that the veteran is assigned the experimental treatment. The regression coefficient c will be tested by a t-test at 5% significance level of c=0 vs. the alternative c $\Box$ 0. Although we believe that c<0 (the treatment reduces presenteeism) we test against inequality because a two-sided test is conservative and conventional.

The primary analysis is "intent to treat" that is, all persons assigned to each group will be followed up to the maximum possible extent, even if they drop out of IC or V-WHI treatment, and analyzed as a part of their assignment group.

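### No reduced contact is planned to secure the T1 primary outcome from veterans who do not complete the full questionnaire of about 45 minutes

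*Combined protocol and SAP*

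**What the plan says.** Section O item 1.2 describes the T1 (month 4 to 5) and T2 (month 9) surveys and how late responders are pursued: "reminder letters are mailed out shortly before each questionnaire is due and, if the person is late in responding, reminder calls will be made". Item 1.4 gives the length: "The baseline and follow-up research questionnaires will take approximately 45 minutes to complete". Table 1 shows what is asked at T1 and T2: the full-form WLQ, the WLQ Time Loss Module, VR-12, PHQ-9, demographics, employment, utilization and cost, disability status, work loss and retention, and CAHPS items.

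Section M item 2.2 plans for "attrition rates of 10% and, in total, 20" per cent at the main site. Section W item 4.1 adds that "we will recruit 250 subjects prior to 50-50 randomization within full time and part time strata". It introduces that number with "To be sure of getting these numbers based on previous success rates".

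Under Aim 1, Hypothesis 1, the primary outcome is the WLQ Productivity Loss score at T1, analysed by intent to treat, and "all persons assigned to each group will be followed up to the maximum possible extent". Section R item 2.3 sets an entry threshold of 5% on the Productivity Loss score and says that presenteeism "will be measured using the WLQ 8-item short form, which is already part of the BHL clinical assessment".

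Other retention steps are telephone or in-person completion, payments of $25 at baseline and T1 and $45 at T2 (Section O item 1.2), one designated contact person (Section R item 9.5.4), and follow-up whether or not the veteran completes the trial (Section T). The text accompanying Table 2 also says that drop-out will be monitored and corrective action taken.

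**The concern.** The primary analysis needs one score from a battery of many instruments. The retention steps help to find or motivate a veteran, but none makes the task smaller. Someone who takes the reminder call but will not give 45 minutes has no described route to answer the WLQ alone, or even to say whether they still have a job. That falls short of the follow-up aim stated for the primary analysis.

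The outcome is self-reported and the veterans know their assignment, so non-response may depend on both arm and work functioning. The Sensitivity Testing section recognises that differential drop-out can bias the comparison. Where drop-out looks outcome-related, it relies on assumed values and selection models. An observed score removes the need for such an assumption for that veteran.

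The counselors' four-weekly WLQ readings cannot fill the gap evenly, because they exist only in the V-WHI arm. Employment status matters too. The background reports 15% job loss within six months in an earlier depressed cohort, and the Secondary Analyses section needs job-loss data for its check on self-report bias.

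**Working it through.** **1. Attrition (Section M item 2.2).** 250 × 0.90 = 225 at T1 and 250 × 0.80 = 200 at T2. The plan's figures reproduce exactly: 25 and 50 veterans lost at the main site. No rate is given for the second site (100 veterans).

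**2. Implied SD (Section W item 4.1).** The plan states 83% power with 100 per arm for a 1.2-point difference, and the test is two-sided at 5%. No SD is given. Solving the two-sample t-test power formula for the SD that yields 83% gives about 2.90 (2.91 with the normal approximation). This is carried forward as an assumption.

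**3. Power with and without recovery (main site, SD 2.90).** The share of non-responders who would accept a short contact is not in the documents; 30% to 60% is an assumed range.

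| | No recovery | 30% recovered | 60% recovered | All recovered |
|---|---|---|---|---|
| T1 n | 225 | 225 + 7.5 = 232.5 | 225 + 15 = 240 | 250 |
| T1 power | 87% | 88% | 89% | 90% |
| T2 n | 200 | 200 + 15 = 215 | 200 + 30 = 230 | 250 |
| T2 power | 83% | 86% | 88% | 90% |

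Even full recovery adds only about 3 points of power at T1.

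**4. Bias.** Let m be the missing share, equal in both arms, and D the amount by which the treatment effect among the missing differs from that among responders after modelling. The bias is m × D. If a share r of the missing is recovered, and those recovered are typical of all non-responders, it becomes m × (1 − r) × D.

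| D (assumed) | T1 bias, m = 0.10 | T1, r = 30% to 60% | T2 bias, m = 0.20 | T2, r = 30% to 60% |
|---|---|---|---|---|
| 1 point | 0.10 | 0.07 to 0.04 | 0.20 | 0.14 to 0.08 |
| 3 points | 0.30 | 0.21 to 0.12 | 0.60 | 0.42 to 0.24 |

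Against the 1.2-point target, the unrecovered T1 bias is 0.10/1.2 = 8% for D = 1 and 0.30/1.2 = 25% for D = 3. To cancel a 1.2-point effect completely, D would have to be 1.2/0.10 = 12 points at T1 or 1.2/0.20 = 6 points at T2.

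**5. Risk from mixing WLQ forms.** Suppose 8-item use differs between arms by 5 percentage points and the two forms differ in level by 1 point (both assumed). The treatment coefficient then shifts by 0.05 × 1 = 0.05 points.

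**The case against.** **Attrition is already planned for.** The 83% power is stated after drop-out, and covariate adjustment, propensity scores and selection models are foreseen. This stands, and it is why the power argument is weak. It does not answer the bias argument, since those methods need assumptions that the data cannot test.

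**The long survey may not be the cause.** A reader might infer that the 45 minutes produce the 10% and 20% losses. The documents do not say so; the recruitment number rests on previous success rates. Veterans who cannot be found or who refuse all contact gain nothing from a shorter form, so the amount recoverable is unknown.

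**The two forms may not agree.** A reader might also infer that the 8-item form gives the same score as the full form. The documents use it only at screening, set the full form for T0, T1 and T2, and nowhere say that the two are interchangeable. Short-form follow-up scores set against a full-form baseline could carry a level difference into the treatment coefficient. On the assumptions in step 5 of the working this is small, and asking the full-form items first largely avoids it.

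**A short option could displace full surveys.** That would cost absenteeism, PHQ-9 and VR-12 data. This stands, so the option has to be held back until the full survey has failed.

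**The plan leaves room for such a step.** It promises corrective action on drop-out and does not say that partial surveys are rejected. Both are true, but neither sets out a minimum data set or how it would be obtained.

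**Conclusion.** The point holds as a gap in the retention plan; it is not a contradiction or an error in the sample size. No reduced contact is described for the primary outcome at T1, where 10% are expected to be missing, or for its repeat at T2, where 20% are. The 20% should not be read as loss of the primary endpoint: the primary time point is T1, and T2 is a sub-hypothesis. Both rates are planning figures for the main site.

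The benefit is mainly less reliance on untestable missing-data assumptions: 0.1 points of T1 bias avoided per 1-point unmodelled arm difference if every missing score were recovered, and proportionally less with partial recovery. This assumes that recovered veterans resemble the other non-responders; if they resemble responders, the bias falls less. The T1 power gain is one to two points at the implied SD of 2.90. The recovery range and the values of D are illustrations, not figures from the plan. The low cost makes the change worth making.

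**What to change.** Add to Section O item 1.2, for both arms identically: if the full T1 or T2 questionnaire has not been completed after the reminders, the reminder call offers a short contact limited to current employment status and hours and the WLQ. The full-form WLQ items used at baseline are asked first, and the 8-item form is offered only if those are declined. The option is not mentioned before the full survey has failed. The form used is recorded, and the text states whether the visit payment applies.

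Add to Section W item 4.2: full-form WLQ scores obtained this way enter the intent-to-treat primary analysis, and results are reported with and without any 8-item scores, because equivalence of the two forms is not documented. The text should also say how a veteran who no longer has a job is handled, since the WLQ may not be scorable and the plan gives no rule.

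The cost is a wording amendment and some minutes on a call that is already made, with no added visits. The downside is that a few scores may come from a noisier form.

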### Table 1.

\* Neuropsych testing may be completed at Baseline if time allows during the visit

Page 14 of 42

- 2.1.3. exact location where data will be collected, BHL Clinic, MIRECC Room B228; research assessments (baseline, T1, T2) will be entered electronically on the Data Management Unit (DMU), a secure electronic database with access restricted to approved research staff members. The DMU will reside on a VA server at the CMCVAMC; clinical data will be entered on the web-based counselor information system, a secure web-based study information system, which will reside on a server at the CMCVAMC. Note, for several months from 12/16/2015 until 2/26/16, the DMU at the University of Pennsylvania was utilized for new and reconsented participants. VA TVHS baseline research assessments will be collected by the VA TVHS research staff at the VA TVHS in private rooms.
- 2.1.4. exact location where data entry will take place. BHL clinic, MIRECC Room B228; research assessments (baseline, T1, T2) will be entered electronically on the Data Management Unit (DMU) – https://vhaphimulhl2.v04.med.va.gov/dmumain/Default.asp. The DMU is a secure electronic database with access restricted to approved research staff members which will reside at the CMCVAMC; clinical data will be entered on the web-based counselor information system, a secure webbased study information system, which will reside on a server at the CMCVAMC (VHAPHIMIRECC1). VA TVHS data entry will take place in private rooms at the VA TVHS CVAMC and its CBOCs.
- 2.1.5. the "title" of individual(s) collecting the data and analyzing the data, e.g. principal investigator, research coordinator. **Principal Investigator (PI)**, investigators at Tufts, Senior Research Coordinator, Coordinators, Research Assistants, Statisticians/Data Analysts, study therapists/clinicians.
- 2.2. Provide a time line for each aspect of the study.

| D | Task Name                            | Start     | Finish     | Duration   |     | FY | 14 |    | FY15 |         | FY16   |    | FY         |    | FY17       |      |     |     |      |
|---|--------------------------------------|-----------|------------|------------|-----|----|----|----|------|---------|--------|----|------------|----|------------|------|-----|-----|------|
|   | Court (round Cogit                   | Citar.    | 1 111311   | Charlendan | 01  | Q2 | 03 | 04 | Q1   | 02      | 03     | 04 | Q1         | 02 | 03         | 24 C | 1 0 | 2 0 | 3 04 |
| 1 | Phase I. Start-up                    | 12/1/2013 | 3/30/2014  | 4 mos      | l i |    |    |    |      | ·       | ·*···· |    | - h |    | 4 4 |      |     |     |      |
| 2 | Phase II. Counselor Preparation      | 2/1/2014  | 4/2/2014   | 2 mos      |     |    |    |    |      |         |        |    |            |    |            |      |     |     |      |
| 3 | Phase III, RCT Recruitment           | 4/1/2014  | 9/30/2016  | 30 mos     |     |    |    |    |      |         |        |    |            |    |            |      |     |     |      |
| 4 | Phase IV. First Follow-Up            | 7/1/2014  | 1/28/2017  | 31 mos     | 1   |    |    |    |      |         |        |    |            |    |            |      |     |     |      |
| 5 | Phase V. Second Follow-Up            | 12/1/2014 | 6/30/2017  | 31 mos     |     |    |    |    | -    |         |        |    |            |    |            |      |     |     |      |
| 6 | Phase VI. Data Analysis              | 3/30/2014 | 8/29/2017  | 41 mos     |     |    |    |    |      |         |        |    |            |    |            |      |     |     |      |
| 7 | Phase VII. Reporting & Dissemination | 8/1/2017  | 11/30/2017 | 4 mos      |     |    |    |    |      |  |        |    |            |    |            |      |     |     |      |

### **Table 2. Project Timetable**

A 48-month long study is proposed (Table 2). Phase I. Study Start up. In Phase II, Counselor Preparation, 2 months (M4-M5) will be devoted to providing an orientation to the V-WHI study counselors The Tufts team (with WOC status) will plan and implement the V-WHI counselor training program. Training will involve performing pre/post counselor evaluations and filing documents to award counselors who successfully complete the program with continuing education credits. Phase III, RCT Recruitment, will allocate 30 months (M5-M35) for identifying and enrolling eligible, consenting veterans, administering the study baseline questionnaires and providing sufficient time for study subjects to

Page 15 of 42

complete the study intervention. During this phase, the V-WHI counselors will participate by tele-conference in refresher training sessions and weekly supervision. Throughout this phase, veteran recruitment and study participation metrics (including drop-out) will be closely monitored with corrective actions taken as necessary. In Phase IV, 1st Follow-up, involving 31 months (M9-M40), study subjects will complete follow-up questionnaires. In Phase V, 2nd Follow-up lasting 31 months (M13-M44) will complete subject data collection.

- 2.3. Phase V1, Data Analysis, will overlap with Phases II-V and beyond (M5-M46). Phase VII, Write-Up and Reporting, will occur over 4 months (M45-48). Chart/Records/Data Review (retrospective and/or prospective)
  - 2.3.1. Provide the planned or approximate number of charts/records/data to be accessed
    - 2.3.1.1. CMCVAMC N/A
    - 2.3.1.2. Other site N/A
  - 2.3.2. Does this protocol employ an Honest Broker? YES NO
    - 2.3.2.1. If yes, provide name of individual.
    - 2.3.2.2. If no, explain who will access the charts/records.
    - 2.3.2.3. Describe from what database charts/records/data will be accessed.

